Publications and/or presentations that result from this study will not include subject identifiable information.

Time in study 56 days from Baseline visit (day 0)

Study Design

This is a single-center, randomized single-control study. One arm will serve as control and will not receive Celluma LED device treatment. The laterality of the control and test arms will be randomized.

Methods of evaluation

- 1. Fitzpatrick skin typing at baseline including ethnicity
- 2. General medical history and concomitant medications
- 3. Standardized clinical photography
- 4. Investigator assessment of treatment response using applicable scales to include:
 - i. Time to heal
 - ii. Percentage healing
 - iii. Edema iv. Erythema
 - iv. Crusting
 - v. Discoloration
 - vi. Scarring
- 5. Subject assessment of pain, discomfort, and itching post treatment
- 6. Patient diaries
- 7. Adverse event recording

Methods of assessment

Authors note:

Scales used to describe healing in leg ulcers and general or surgical wounds, apart from the Leg Ulcer Measurement Tool LUMT, lack comprehensive and quality evaluation with respect to validity, reliability, and sensitivity. The author has reviewed the Food and Drug Administration's guidelines on wound healing and has identified the following areas that constitute important measurement metrics in wound healing.

Clinical assessment

Clinical photography

Digital clinical photography shall be taken at baseline, immediately post treatment and at each assessment point.

Healing assessment

Clinical assessment shall be performed by independent and blinded assessors, based on visual examination and clinical photography of the test and control areas at baseline (before the first session), and at each assessment point.

Healing shall be graded at each assessment on a 5-point visual analogue scale as follows:

i. Excellent: 81% - 100% healing
ii. Very Good: 61% - 80% healing
iii. Good: 41% - 60% healing
iv. Fair: 21% - 40% healing
v. Little or no change: 0% - 20% healing

Erythema

Clinical assessment shall be performed by independent blinded assessors, based on visual examination and clinical photography of the test and control areas at baseline (before the first session), and at each assessment point.

Erythema shall be graded at each assessment on an 11-point scale as follows:

- i. Little to No Erythema
- 0
- 1

ii. Mild Erythema

- 2
- 3
- 4
- iii. Moderate Erythema
- 5
- 6
- 7

iv. Severe Erythema

- 8
- 9
- 10

Swelling

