Clinical assessment shall be performed by independent and blinded assessors, based on visual examination and clinical photography of the test and control areas at baseline (before the first session), and at each assessment point.

Swelling shall be graded at each assessment on a 11-point scale as follows:

- i. No Swelling evident
- 0
- 1
- ii. Mild Swelling
- 2
- 3
- 4
- iii. Moderate Swelling

- 5
- 6
- 7

iv. Severe Swelling

- 8
- 9
- 10

Crusting

Clinical assessment shall be performed by independent and blinded assessors, based on visual examination and clinical photography of the test and control areas at baseline (before the first session), and at each assessment point.

Crusting shall be graded at each assessment on a 11-point visual analogue scale as follows:

- i. No crusting evident
- 0
- 1

ii. Mild Crusting

- 2
- 3
- 4

iii. Moderate Crusting

- 5
- 6
- 7

iv. Severe Crusting

- 8
- 9
- 10

Subject assessment

Pain

Pain shall be assessed using an 11-point Visual Analogue Scale (VAS) (0-10-point scale). The Scale will be used at the following timepoints.

- i. Immediately after the test area performance
- ii. 30 minutes after the first treatment session of Biophotas Celluma.
- iii. Daily, immediately before and 30 minutes after each Biophotas Celluma treatment.

Discomfort

Discomfort shall be assessed using an 11-point Visual Analogue Scale (VAS) (0-10-point scale). The Scale will be used at the following timepoints.

- i. Immediately after the test area performance
- ii. 30 minutes after the first treatment session of Biophotas Celluma
- iii. Daily, immediately before and 30 minutes after each Biophotas Celluma treatment

Itching

Itching shall be assessed using an 11-point Visual Analogue Scale (VAS) (0-10-point scale). The Scale will be used at the following timepoints.

Daily, immediately before and 30 minutes after each Biophotas Celluma treatment.

STATISTICAL ANALYSIS PLAN

The primary endpoint measured in the study is length of days to reach either a 0 or 1 on the 11-point scale for erythema, swelling, and crusting, as well as 80-100% overall healing on the treatment arm compared to the control arm. Comparisons of pain, discomfort, and itch ratings will also be made between treatment and control arms by calculating the average scores.

Times to full healing and times to resolution of all side effects will be described by frequency distributions together with mean values and associated 95% confidence limits.

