A comparable study of LED therapy involving 10 patients gave mean (SD) treated healing time of 13.5 (1.1) days and mean (SD) untreated healing time of 26.8 (1.6) days. Mean (SD) of relative reduction in healing time was 50% (2.2%) and the lowest relative reduction was 48%. Assuming similar results for the proposed study, the study size of 25 would virtually guarantee statistically significant reductions in healing time. Based on 95% confidence intervals, the mean treated healing time, mean untreated healing time and mean relative reduction in healing time will be estimated with precisions of 3.1%, 2.3% and 1.7%.

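### The analysis text names no within-subject contrast or test: the healing-time effect interval appears only in the sample-size paragraph, and pain, discomfort and itch get a comparison of averages with no interval, test or pairing

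*Combined protocol and SAP*

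**What the plan says.** The Study Design section sets up a within-subject comparison: "One arm will serve as control and will not receive Celluma LED device treatment", and "The laterality of the control and test arms will be randomized". The first paragraph of the Statistical Analysis Plan defines the primary endpoint comparatively, as days until three sign scores are low together with "80-100% overall healing on the treatment arm compared to the control arm".

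The analysis wording is brief. For healing time and resolution of side effects, results "will be described by frequency distributions together with mean values and associated 95% confidence limits". For symptoms, "Comparisons of pain, discomfort, and itch ratings will also be made between treatment and control arms by calculating the average scores".

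The closing sample-size paragraph, under the same heading, takes its inputs from a comparable 10-patient study: "mean (SD) treated healing time of 13.5 (1.1) days" and "mean (SD) untreated healing time of 26.8 (1.6) days", with a relative reduction of 50% (SD 2.2%, lowest value 48%). It concludes that "the study size of 25 would virtually guarantee statistically significant reductions in healing time". It also gives expected 95% precisions of 3.1%, 2.3% and 1.7% for the treated mean, the untreated mean and the mean relative reduction.

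**The concern.** When both arms belong to the same person, the natural effect measure is the contrast within that person, with its own interval and a paired test. The analysis sentences do not state one. The healing-time sentence names no arm, no difference and no test. An analyst could report two means with two sets of limits and comply with it fully. The significance forecast in the sample-size paragraph has no test behind it, and no significance level is given.

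The gap is wider for symptoms. The Background section hypothesises both less pain and faster healing, and the protocol names pain as a secondary outcome. The plan for it stops at averages by arm, and does not say whether these are taken over subjects, time points or both. Two averages without a measure of uncertainty cannot support a conclusion about pain in either direction.

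**Working it through.** **1. Reproduce the plan's precisions.** Inputs are the planning means and SDs and n = 25, all from the sample-size paragraph. Relative half-width = 1.96 × SD / √25 / mean.

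| Quantity | Calculation | Result | Stated |
|---|---|---|---|
| Treated mean | 1.96 × 1.1 / 5 / 13.5 | 3.19% | 3.1% |
| Untreated mean | 1.96 × 1.6 / 5 / 26.8 | 2.34% | 2.3% |
| Mean relative reduction | 1.96 × 2.2 / 5 / 50 | 1.72% | 1.7% |

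The second and third agree. The first would round to 3.2%, but 3.1% lies within the range 3.04% to 3.35% allowed by rounding of the mean and SD. Using t on 24 df gives 3.36%, 2.46% and 1.82%, a poorer fit.

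**2. Does the 1.7% use the pairing?** The coefficients of variation are 1.1/13.5 = 0.0815 and 1.6/26.8 = 0.0597. The ratio of means is 13.5/26.8 = 0.504. If the arms were independent, the delta-method SD of the ratio would be 0.504 × √(0.0815² + 0.0597²) = 0.051, and the precision 1.96 × 0.051/5/0.50 ≈ 4.0%. The stated 1.7% follows only from the SD of 2.2%, which belongs to a quantity calculated subject by subject. So the pairing is used there.

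**3. Implied correlation and interval in days.** The documents give no correlation, so it is back-calculated. The coefficient of variation of the ratio is 0.022/0.504 = 0.0437. Then ρ = (0.0815² + 0.0597² − 0.0437²)/(2 × 0.0815 × 0.0597) ≈ 0.85 (0.84 to 0.86 over rounding of the 2.2%).

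- SD of the difference: √(1.21 + 2.56 − 2 × 0.853 × 1.1 × 1.6) = 0.88 days.
- Paired 95% half-width (t, 24 df): 2.064 × 0.877/5 = 0.36 days.
- Half-width ignoring the pairing (t, 48 df): 2.011 × √(3.77/25) = 0.78 days.
- If ρ is instead assumed to lie between 0 and 0.9, the paired half-width runs from 0.80 to 0.32 days.

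**4. Does this matter for power?** The planning difference is 26.8 − 13.5 = 13.3 days. Even at ρ = 0 the SD of the difference is √3.77 = 1.94 days, and 13.3/(1.94/5) is about 34 standard errors. Power is essentially 100% with or without pairing.

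**5. Symptoms.** The documents give no SD, correlation or expected effect for pain, discomfort or itch, so no size can be calculated. The finding there rests on the text alone: averages are compared, and nothing further is specified anywhere.

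**The case against.** A reader might infer from the analysis sentences that the plan discards the pairing and gives no interval for the treatment effect. The documents do not support that for healing time. The sample-size paragraph stands under the same heading and commits to estimating the mean relative reduction with 95% confidence, and step 2 shows that its precision depends on within-subject data. Nor does the plan anywhere say that the effect will be judged by an unpaired test or by whether two per-arm intervals overlap. The healing-time sentence does not even mention arms separately. This part of the objection stands in full.

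The objection also stands on size. Half-widths of 0.36 and 0.78 days are both trivial beside 13.3 days. They come from a correlation inferred from a 10-patient study. They also suggest a finer resolution than assessments on days 2, 4, 6, 9, 13, 20, 27, 34 and 55 may allow. Carrying the roughly twofold difference in width over to symptom scores would be unsupported.

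What the objection does not answer is the missing method. A precision forecast does not state a primary analysis. It leaves open whether the result rests on the relative reduction or the difference in days, and which test decides it. For symptoms there is no counterpart in the sample-size text to fall back on.

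**Conclusion.** The point holds as a gap in specification for healing time and as an inadequate stated method for pain, discomfort and itch. For healing time, a paired effect interval exists in the plan but outside the analysis text, and the forecast of significance has no test attached. For symptoms, there is no interval, test or use of the pairing, and the pain part of the hypothesis cannot be concluded from what is written.

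No effect on the sample size or on primary power is claimed. The correlation of about 0.85 and the two half-widths in days rest on the planning SDs and a delta-method approximation, and apply to healing time only. The change is worth making because it costs almost nothing and because the symptom comparison needs it.

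**What to change.** Rewrite the analysis paragraph of the Statistical Analysis Plan as follows.

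- **Healing time:** state the mean within-subject relative reduction with its 95% confidence interval as the effect measure, as the sample-size paragraph already foresees. Add the within-subject difference in days (control minus test) with its interval. Name one two-sided 5% paired test in advance. Wilcoxon signed-rank is a reasonable choice, because times are recorded on visit days and will be coarse and often tied.
- **Pain, discomfort and itch:** replace the comparison of averages with per-subject test-minus-control differences, reported with mean, 95% confidence interval and a paired test. Say which time points enter each subject's score.
- **Per-arm means and frequency distributions:** keep as description.

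The cost is one paragraph. It needs no more subjects. It needs no new data either, provided symptoms are scored separately for each site, which the plan's own comparison between arms already presupposes.

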- 1. Subjects will return to the clinic on days 2, 4, 6, 9, 13, 20 and 27. * Scheduled follow-up visits may be adjusted 1-2 days based on clinic or patient availability.
- 2. The subject will be questioned generally to ascertain any changes in health or concomitant medication.
- 3. The subject's diary will be reviewed, and the subject will be questioned to ascertain any potential adverse incidents.
- 4. Clinical digital photography of test and control site will be recorded.
- 5. The Investigator will assess both test and control sites using visual analogue scales to include time to heal, percentage healing, edema, erythema, swelling and crusting.
- 6. Subject will assess treatment response using a grading of response.
- 7. The subject will be given a date and time to return to the clinic for the next assessment.

Day 34

- 1. The subject will be questioned generally to ascertain any changes in health or concomitant medication.
- 2. Clinical digital photography of test and control site will be recorded.
- 3. The Investigator will assess both test and control sites using visual analogue scales to include time to heal, percentage healing, edema, erythema, swelling and crusting.
- 4. Subject will assess treatment response using a grading of response.
- 5. The subject will be given a date and time to return to the clinic for the last assessment.

Day 55

- 1. The subject will be questioned generally to ascertain any changes in health or concomitant medication.
- 2. Clinical digital photography of test and control site will be recorded.
- 3. The Investigator will assess both test and control sites using visual analogue scales to include time to heal, percentage healing, edema, erythema, swelling and crusting.
- 4. Subject will assess treatment response using a grading of response. If there are no continuing adverse events and the patient has completed all diaries, they will be allowed to keep the Celluma device, and signed off the study.

Digital photographs will be taken of each ventral arm from antecubital fossa to axilla before laser application, directly after laser application, and at designated assessment visits in clinic. The photos will only include the ventral arm in the frame. If there are tattoos present in the area they will be covered using a black photography cloth or blue medical drape.

Subject will be asked to give consent prior to participating in the study by signing an informed consent form and photography release form.

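### The precisions stated for n = 25 (3.1%, 2.3%, 1.7%) make no allowance for visits 4 to 7 days apart where healing is expected, and no rule fixes the recorded healing day

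*Combined protocol and SAP*

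**What the plan says.** The first paragraph of the SAP defines the primary endpoint as the "length of days to reach either a 0 or 1 on the 11-point scale for erythema, swelling, and crusting", together with overall healing of 80 to 100%. The next paragraph says "Times to full healing and times to resolution of all side effects will be described by frequency distributions together with mean values" and 95% confidence limits.

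The study-size paragraph takes from an earlier 10-patient study a "mean (SD) treated healing time of 13.5 (1.1) days", a "mean (SD) untreated healing time of 26.8 (1.6) days", and a mean (SD) relative reduction of 50% (2.2%). It continues "Assuming similar results for the proposed study", and concludes that 25 subjects virtually guarantee significance and that the mean treated time, mean untreated time and "mean relative reduction in healing time will be estimated with precisions of 3.1%, 2.3% and 1.7" per cent.

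Under Methods of assessment, "Healing shall be graded at each assessment on a 5-point visual analogue scale as follows"; erythema, swelling and crusting are also graded at each assessment. In the Study Narrative, "Subjects will return to the clinic on days 2, 4, 6, 9, 13, 20 and 27", followed by days 34 and 55, and day 62 if a site is still unhealed. The daily diary covers pain, discomfort, itching and the treatment log, not healing. Time to heal is listed among the investigator's items at each visit, but no text says how a day is arrived at.

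**The concern.** A site that meets the criteria on day 14 is not graded until day 20. The data show only that healing fell between two visits, and the recorded day depends on a convention that the SAP does not state. Where healing is expected, the gaps are 4 days (9 to 13) and 7 days (13 to 20, 20 to 27, 27 to 34). The SDs carried over from the earlier study are 1.1 and 1.6 days. Recorded days that can take only a few widely spaced values can vary much more than that.

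Two things are at stake. First, the SAP promises a precision that its own assumptions do not deliver under this schedule. Second, the headline estimates move with the convention. A treated mean near 17.7 days and a reduction near 41% could be read against the 13.5 days and 50% of the earlier study as a weaker effect, when much of the difference comes from when sites were examined. With no rule in the SAP, the convention could also be chosen after the data are seen.

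**Working it through.** **Inputs (SAP, study-size paragraph).** n = 25; treated 13.5 (1.1) days; untreated 26.8 (1.6) days; reduction 50% (2.2%). Visit days are from Research Procedures.

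**1. The plan's own figures.** Half-width as a percentage of the mean = 1.96 × SD / √25 / mean.
- Treated: 1.96 × 1.1 / 5 / 13.5 = 3.19%
- Untreated: 1.96 × 1.6 / 5 / 26.8 = 2.34%
- Reduction: 1.96 × 2.2 / 5 / 50 = 1.72%

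These match 3.1%, 2.3% and 1.7% when cut to one decimal. There is no term for visit spacing.

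**2. Where healing falls (normal times).**
- Treated by day 13: Φ((13 − 13.5)/1.1) = Φ(−0.455) = 0.325. The other 0.675 are first seen healed on day 20.
- Untreated by day 27: Φ((27 − 26.8)/1.6) = Φ(0.125) = 0.550. The other 0.450 are first seen healed on day 34.
- A negligible share falls outside days 9–20 (treated) and 20–34 (untreated).

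**3. Within-subject correlation.** Ratio of means 13.5/26.8 = 0.504; coefficients of variation 1.1/13.5 = 0.0815 and 1.6/26.8 = 0.0597. Setting 0.504 × √(0.0815² + 0.0597² − 2ρ × 0.0815 × 0.0597) = 0.022 gives ρ = 0.853.

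**4. Recorded day = first visit at which the criteria are met.**
- Treated: mean 13 × 0.325 + 20 × 0.675 = 17.7; SD 7 × √(0.325 × 0.675) = 3.28; precision 1.96 × 3.28 / 5 / 17.7 = 7.2% (unrounded inputs)
- Untreated: mean 27 × 0.550 + 34 × 0.450 = 30.2; SD 7 × √(0.550 × 0.450) = 3.48; precision 4.5%
- Reduction, by simulation of pairs at ρ = 0.853:

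| Recorded days (treated, untreated) | Share | Reduction |
|---|---|---|
| 13, 27 | 30.9% | 51.9% |
| 13, 34 | 1.6% | 61.8% |
| 20, 27 | 24.1% | 25.9% |
| 20, 34 | 43.4% | 41.2% |

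The mean is 41.1% and the SD 9.9 points, so the precision is 1.96 × 9.9 / 5 / 41.1 = 9.4%.

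**5. Recorded day = interval midpoint.**
- Treated: 11 × 0.325 + 16.5 × 0.675 = 14.7; SD 5.5 × 0.468 = 2.58; 6.9%
- Untreated: 23.5 × 0.550 + 30.5 × 0.450 = 26.7; SD 3.48; 5.1%
- Reduction: mean 45%, SD 9.1 points; 8.0%

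**6. Summary.**

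| | Treated | Untreated | Reduction |
|---|---|---|---|
| Stated | 3.1% | 2.3% | 1.7% |
| First healed visit | 7.2% | 4.5% | 9.4% |
| Midpoint | 6.9% | 5.1% | 8.0% |

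**7. A bound free of the normal assumption.** If recorded days are scheduled visit days and their mean is 13.5, the SD is smallest when all values are 13 or 20: √((20 − 13.5)(13.5 − 13)) = √3.25 = 1.80 days. Treated precision is then at least 1.96 × 1.80 / 5 / 13.5 = 5.2%. For midpoints (11 or 16.5) the minimum SD is √(3 × 2.5) = 2.74 days. The same bound for the untreated mean is √((26.8 − 20)(27 − 26.8)) = 1.17 days, or 1.7%, so it does not exclude the stated 2.3%.

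**8. Sensitivity.** With correlation from 0 to 0.9, the reduction's precision is 9.2–12.6% (first healed visit) and 7.8–10.9% (midpoint). With other means, same SDs and ρ = 0.853 (illustrative):

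| Means (days) | Ignoring visits | First healed visit | Midpoint |
|---|---|---|---|
| 11, 23.5 | 3.9, 2.7, 1.9% | 4.5, 1.7, 3.8% | 4.3, 2.0, 3.4% |
| 15, 30 | 2.9, 2.1, 1.6% | 2.5, 2.4, 3.7% | 2.4, 2.1, 2.9% |
| 16.5, 40 | reduction 1.1% | reduction 0.3% | reduction 0.3% |

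**9. Significance.** The mean paired difference is 12.4 days with SD 3.19 (first healed visit), so t ≈ 12.4 / (3.19/5) ≈ 19.5. For midpoints it is 11.9 / (2.96/5) ≈ 20.

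**The case against.** The strongest reply is that the stated figures are correct for their inputs and expressly conditional on similar results. The earlier study's assessment schedule is not given, so its SDs may already contain visit rounding, and adding this trial's spacing on top could count it twice. That uncertainty stands for the untreated mean. It does not rescue the treated figure: on this trial's scheduled days a recorded mean of 13.5 cannot go with an SD of 1.1.

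A second reply is that counting days until criteria are met, when the criteria are graded at visits, naturally means the first visit at which they are met. I accept that. A reader might add the last unhealed visit as a third candidate (treated mean 11.7 days, reduction 49%) and so widen the range of possible answers, but that rule would date healing to a day on which the site was graded unhealed, which does not fit the endpoint. Even the natural reading leaves the stated precisions unmet.

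Third, the replacement figures are sensitive. The assumed means lie 0.5 and 0.2 days from visits 13 and 27, where the split between two visits matters most. This stands: at other means the precision can be better or worse, and it should not be said that visit spacing always worsens it.

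Fourth, the SAP already plans frequency distributions, which carry much of the visit-level information. That also stands, and replacing the means by proportions or sign tests would be a matter of preference.

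Finally, a reader might infer that the allowance to move visits by 1–2 days adds to the problem. It is starred only for days 2, 4 and 6, none of which is a visit where healing is expected.

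**Conclusion.** The point holds, as a fault in what the stated precisions assume and not in how they were calculated. On the plan's own means and SDs, the precision under the first-healed-visit reading is about 2.3 times wider than stated for the treated mean (7.2/3.1), 2.0 times for the untreated mean (4.5/2.3) and 5.5 times for the reduction (9.4/1.7). With midpoints the factors are about 2.2, 2.2 and 4.7. This rests on normal healing times, visits on their scheduled days, a correlation of 0.853 derived from the stated 2.2% SD, and means close to visits 13 and 27. The bound of 5.2% for the treated mean needs only a recorded mean of 13.5 on scheduled days.

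A reader might infer that the trial is too small or that its comparison is unsafe. The documents do not support that. The paired t statistic stays near 20, so the claim about significance stands on the plan's assumptions. Nor is the planned confidence interval unsound: simulated coverage for the mean of the recorded day is 93–96%. What fails is the stated precision, and the recorded day needs defining. This should be fixed before analysis. Confidence is high that the rule and the allowance are missing, and lower for the exact replacement values.

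**What to change.** 1. State in the SAP that the healing day is the first assessment at which all criteria are met, or another rule fixed in advance, using the actual visit date. Record the last unhealed visit as well. Say that the reported mean is the mean of that recorded day and that, under the first-healed-visit rule, it overstates true healing time.
2. Replace 3.1%, 2.3% and 1.7% with the precisions for the chosen rule, stated as conditional on the assumed means of 13.5 and 26.8 days: about 7.2%, 4.5% and 9.4% for first healed visit. Alternatively, keep the present figures and label them as ignoring visit spacing.
3. Optionally, add an interval-censored estimate per arm as a sensitivity analysis beside the frequency distributions already planned.

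The cost is SAP wording, a little more analysis and a less favourable stated precision. No extra subjects or visits are needed.

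### The stated precisions assume healing is known to the exact day; with grading only at scheduled visits, the intervals would be about two to six times wider

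*Combined protocol and SAP*

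**What the plan says.** The last paragraph of the Statistical Analysis Plan takes its planning values from a 10-patient LED study: "mean (SD) treated healing time of 13.5 (1.1) days and mean (SD) untreated healing time of 26.8 (1.6) days". It adds "Mean (SD) of relative reduction in healing time was 50% (2.2" per cent). On the premise that this trial behaves similarly, it concludes that "the study size of 25 would virtually guarantee statistically significant reductions in healing time". It then states, "Based on 95% confidence intervals", that the three means "will be estimated with precisions of 3.1%, 2.3% and 1.7" per cent. It does not define precision, and it does not say whether a normal or a t multiplier was used.

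The primary endpoint, set out in the first paragraph of the SAP, is the number of days until erythema, swelling and crusting each score 0 or 1 and overall healing reaches the top band. Under Methods of assessment, blinded assessors grade all four components at each assessment point. The Study Narrative fixes those points: "Subjects will return to the clinic on days 2, 4, 6, 9, 13, 20 and 27". Further assessments follow on days 34 and 55, and on day 62 if a site is still unhealed. The SAP also commits to reporting mean times to healing with 95% confidence limits, so these intervals will appear in the results.

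**The concern.** The precision figures treat healing time as a continuous quantity with a spread of one to two days. The visits around the expected healing times are mostly a week apart: days 13 and 20 on either side of most treated sites, and days 20, 27 and 34 around the untreated ones. The protocol gives no rule for placing a healing day between two visits. A time that can take only a few values a week apart has a much larger SD than 1.1 or 1.6 days, and its mean may shift as well.

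What is at stake is how accurately the SAP describes what the trial will deliver. The reported intervals would be well wider than stated, and the headline relative reduction could differ from 50% because of the visit calendar alone.

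There are two smaller points. The first figure is off in its last digit. The third can be misread, because a percentage precision on a quantity already in per cent may be taken as percentage points.

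**Working it through.** **Inputs.** From the SAP: treated 13.5 (1.1) days, untreated 26.8 (1.6) days, relative reduction 50% (2.2 points), n=25, 95% intervals. From the Study Narrative: visits on days 2, 4, 6, 9, 13, 20, 27, 34 and 55. Assumed here: normally distributed healing times, visits on their nominal days, and a within-subject correlation of 0.85.

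**1. Reproducing the plan's figures.** Relative half-width = 1.96 × SD / √25 / mean.
- Treated: 1.96 × 1.1 / 5 / 13.5 = 3.19% (stated 3.1%)
- Untreated: 1.96 × 1.6 / 5 / 26.8 = 2.34% (stated 2.3%)
- Relative reduction: 1.96 × 2.2 / 5 = 0.862 points; 0.862 / 50 = 1.72% (stated 1.7%)

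All three agree if cut to one decimal. With ordinary rounding the first would be 3.2%. The third reproduces only as a percentage of 50%.

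**2. With t on 24 df (2.064), since the SDs will be estimated.** Treated ±0.454 days (3.36%), untreated ±0.660 days (2.46%), reduction ±0.908 points (1.82% of 50%).

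**3. The correlation.** With CVs of 1.1/13.5 = 0.0815 and 1.6/26.8 = 0.0597, the SD of the ratio is approximately 0.504 × √(0.0815² + 0.0597² − 2 × 0.85 × 0.0815 × 0.0597) = 0.022. So 0.85 reproduces the plan's own SD of 2.2 points. The results for the two healing times do not depend on it.

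**4. Healing dated to the first visit at or after it.**
- Treated: P(time ≤ 13) = Φ((13 − 13.5)/1.1) = 0.325, so about 32% are recorded on day 13 and 68% on day 20. Mean = 13 × 0.325 + 20 × 0.675 = 17.7. SD = 7 × √(0.325 × 0.675) = 3.28. Precision = 2.064 × 3.28 / 5 / 17.7 = 7.6% (±1.35 days).
- Untreated: P(time ≤ 27) = Φ((27 − 26.8)/1.6) = 0.550, so about 55% are recorded on day 27 and 45% on day 34. Mean = 27 × 0.55 + 34 × 0.45 = 30.15. SD = 7 × √(0.55 × 0.45) = 3.48. Precision = 2.064 × 3.48 / 5 / 30.15 = 4.8% (±1.44 days).
- Relative reduction, by simulation: mean 41.1%, SD 9.9 points. Precision = 2.064 × 9.9 / 5 = 4.1 points; 4.1 / 41.1 = 9.9%, about 10%. Over correlations from 0 to 0.95 it lies between about 9.5% and 13%.

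**5. Healing dated to the midpoint of the visit interval.**
- Treated values are 11 (days 9 to 13) or 16.5 (days 13 to 20). Mean = 11 × 0.325 + 16.5 × 0.675 = 14.7. SD = 5.5 × √(0.325 × 0.675) = 2.58. Precision = 2.064 × 2.58 / 5 / 14.7 = 7.2%.
- Untreated values are 23.5 or 30.5. Mean = 23.5 × 0.55 + 30.5 × 0.45 = 26.65. SD = 3.48. Precision = 5.4%.
- Relative reduction, by simulation: mean about 45% (44.5%), SD 9.1 points. Precision = 2.064 × 9.1 / 5 / 44.5 = 8.4%.

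| | Treated | Untreated | Relative reduction |
|---|---|---|---|
| Stated | 3.1% | 2.3% | 1.7% |
| Exact day, z | 3.19% | 2.34% | 1.72% |
| Exact day, t | 3.36% | 2.46% | 1.82% |
| First visit | 7.6% | 4.8% | about 10% |
| Midpoint | 7.2% | 5.4% | 8.4% |

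**6. A check free of the normality assumption.** If recorded times can only be visit days, a mean of 13.5 has its smallest SD when all values are 13 or 20, with 0.5/7 = 0.071 of them at 20. That SD is 7 × √(0.071 × 0.929) = 1.8 days. Recorded visit days therefore cannot have both the planning mean of 13.5 and the planning SD of 1.1.

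**The case against.** The strongest reply is that the paragraph is conditional. It assumes results like those of the earlier study, and on that premise its arithmetic is sound. This stands. A reader might infer that the three figures do not follow from the plan's own inputs, but the documents do not support that. Two match under ordinary rounding. The third discrepancy is 3.19% printed as 3.1%, and rounding of the published inputs (SD 1.05 to 1.15, mean 13.45 to 13.55) allows 3.04% to 3.35%. Using z rather than t is a common planning approximation, and replacing it moves the half-widths only from 0.431 to 0.454 days and from 0.627 to 0.660 days.

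A reader might also infer that these precisions are the only quantitative support for n=25, or that 25 is too few. Neither follows. The same paragraph argues first from the expected difference. On its inputs the difference divided by its standard error is 13.3 / (√(1.1² + 1.6²) / 5) = 34 at zero correlation. On the visit grid the ratio is still about 19 at correlation 0.85 and 13 at zero.

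It can fairly be said that the visit-grid figures rest on a dating rule the documents do not state. That is why two rules are shown; both give intervals at least twice as wide as stated. The investigator is also asked to rate time to heal, and subjects keep a diary. But no passage says how a day between visits would be derived, and the diary covers pain, discomfort, itching and site symptoms rather than the blinded endpoint grades. The allowance to move visits by one or two days is marked against days 2, 4 and 6. Even if it applied to every visit, it would not turn gaps of a week into exact days.

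**Conclusion.** The concern holds for what the SAP says the trial will deliver. It does not hold as a charge of faulty calculation. The stated precisions describe healing times observed to the exact day, and the planned assessments do not observe them that way. Under either dating rule the relative half-widths are a little over twice those stated for the two healing times (7.6/3.1 = 2.5 and 4.8/2.3 = 2.1 with first-visit dating; 7.2/3.1 = 2.3 and 5.4/2.3 = 2.3 with midpoint dating). For the relative reduction they are about five to six times those stated (8.4/1.7 = 4.9; 9.9/1.7 = 5.8). The recorded reduction would be about 41% or 45% rather than 50%.

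The sizes depend on normal times with the planning means and SDs, visits on nominal days and, for the relative reduction only, the correlation. The last-digit slip and the choice of z over t are minor. The case for n=25 on statistical significance is not affected.

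**What to change.** Revise the final paragraph of the SAP as follows.

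1. Define precision as the half-width of the 95% confidence interval divided by the mean.
2. Restate the exact-day values for n=25 with t on 24 df: treated mean ±0.45 days (3.4%), untreated mean ±0.66 days (2.5%), relative reduction ±0.9 percentage points (1.8% of 50%). If the normal approximation is kept instead, correct 3.1% to 3.2%.
3. Say that these values assume healing times known to the exact day.
4. State the rule by which a healing day is assigned from the visit grades, and give the precisions under that rule, with their assumptions, as what the design will deliver: about 7.6%, 4.8% and 10% for first-visit dating, or about 7.2%, 5.4% and 8.4% for midpoint dating. Give the expected recorded reduction alongside (about 41% or 45%).

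The change is to SAP wording only. It leaves the sample size at 25 and the visit schedule as it is. The cost is that the stated figures become less favourable.
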